11.1.3.1. Lipid and Metabolic Panel, Glycated Hemoglobin, and Lipoprotein Particle Size

A fasting blood sample for lipid and metabolic panels as well as HbA1c is to be collected at the time points designated in Table 2. The following parameters are to be determined:

- **Lipid Panel:** LDL-C, non-LDL-C, HDL-C, non-HDL-C, total cholesterol, TG, ApoB, and Lp(a) particles

- **Metabolic Panel:** Glucose, insulin, NEFA, and GGT. HOMA2-IR and adipo-IR are to be calculated from fasting insulin, fasting glucose, and fasting NEFA, as applicable
- **Hb1Ac**
- **Lipoprotein Particle Size Analysis** by nuclear magnetic resonance (NMR)

Subjects are to fast overnight for at least 9 hours prior to collection of the fasting sample. (Water is permissible.)

11.1.3.2. NASH / Fibrosis Markers

A blood sample for NASH / fibrosis markers, including CK-18, FIB-4 Index, ELF (TIMP-1, PIIINP, HA), PROC3, and FIBROSpect 2, is to be collected at the time points designated in [Table 2](#). Instructions regarding the calculation of indices are provided in the Operations Manual.

11.1.3.3. Eicosanoid Panel

A blood sample for an eicosanoid panel, including 5-LOX–derived leukotriene B4 (LTB4), COX-derived prostaglandin E2 (PGE2), and 15-LOX–derived 15-hydroxyeicosatetraenoic acid (15-HETE) and lipoxin A4 (LXA4), is to be collected at the time points designated in at the time points designated in [Table 2](#).

11.1.3.4. Inflammatory Biomarkers

A blood sample for inflammatory biomarkers, including tumor necrosis factor-alpha (TNF α), interleukin (IL)-6, IL-8, high-sensitivity C-reactive protein (Hs-CRP), monocyte chemoattractant protein-1 (MCP-1), is to be collected according to the time points in [Table 2](#).

11.1.3.5. Adiponectin, Resistin, Leptin

A blood sample for determination of adiponectin, resistin, and leptin, is to be collected according to the time points in [Table 2](#), with these parameters determined using enzyme-linked immunosorbent assay (ELISA).

11.1.4. Lipidomic Analyses

In the current study, a fasting blood sample for fatty acid analyses will be collected according to the time points in [Table 2](#). Plasma TG will be isolated from the blood. The quantity and composition of fatty acids in these TGs will be evaluated. The quantity and composition of fatty acids in these TGs will be evaluated. The quantity of palmitate (C16:0) in this fraction, representing hepatic synthesized lipid, will be compared to the quantity of omega-6-linoleic acid (C18:2n6), an essential fatty acid obtained through dietary sources. Decreased ratios of C16:0 / C18:2n6 are indicative of decreased hepatic lipogenesis ([Hudgins, 1996](#)).

11.1.5. Genomics

A blood sample for genomics pertaining to the disease under study will be collected at the time points designated in [Table 2](#); subjects will be asked to provide separate written informed consent for the collection of such samples.

11.1.6. Sample Collection for Storage

Blood and spot urine samples for storage will be collected at the time points designated in [Table 2](#). These samples will be stored for the duration of the TVB-2640 clinical development program and used for analysis of additional pharmacodynamic biomarkers relevant to NAFLD and/or NASH when such biomarkers are identified and/or relevant assays are developed.

These samples will not be used for genetic analysis nor creation of cell lines. The biomarker assessments performed may include tests to determine the level of certain proteins, RNA or other disease related molecules and whether they change after TVB-2640 treatment.

The samples will be coded and de-identified, in the same way all other study samples are coded and de-identified. Every study subject has a unique study number that will be used to track the samples. The subject's confidentiality will be maintained and will not be made publicly available to the extent permitted by the applicable laws and regulations.

The Sponsor and/or its designee and the Regulatory Authorities will have access to the samples/data if they are ever used for a future research.

The collection of blood and spot urine samples for storage is not voluntary and will be collected for all subjects randomized to the study.

11.1.7. Anthropometric Assessments

Anthropometric assessments are to be performed at the time points designated in [Table 2](#), including:

- Weight (without shoes or heavy clothing) (kg), with calculation of BMI using screening height and weight.
- Waist circumference at umbilicus (cm)
- Hip circumference (cm)
- Waist-hip ratio

11.1.8. Lymphocyte Subsets in Peripheral Blood Mononuclear Cells

Blood samples are to be collected from a subset of subjects enrolled at selected study centers at baseline and Week 12 for exploratory evaluation of change in CD4/Th17/regulatory T-cell populations and, potentially, natural killer-T and epigenetic or activation changes in peripheral blood mononuclear cells.

11.2. Pharmacokinetic Assessments

[REDACTED]

[REDACTED]

[REDACTED]

[REDACTED]

[REDACTED]

[REDACTED]

[REDACTED]

The times of study drug administration, the most recent meal prior to blood sample collection, and of blood sample collection are to be documented in the eCRF.

[REDACTED]

12. ASSESSMENT OF SAFETY

12.1. Safety Parameters

12.1.1. Vital Signs

Vital signs, including oral temperature (°C), pulse (bpm), systolic and diastolic blood pressure (mmHg), and respiration rate (breaths/minute), are to be measured and documented in the eCRF at the time points designated in [Table 2](#). Measurements are to be made after the subject has been resting in a supine position for a minimum of 5 minutes.

12.1.2. Physical Examination and Height

A complete physical examination will be conducted for all subjects at the time points designated in [Table 2](#). The complete physical is to include examination of general appearance, head/ears/eyes/nose/throat, lungs/chest, heart, abdomen, lymph nodes, musculoskeletal, extremities, skin, and neurological examination. Liver signs (jaundice, spider angiomas, palmar erythema, hepatomegaly, splenomegaly, asterixis) also are to be assessed.

During screening, the physical examination is to include measurement of height (cm).

Abbreviated (i.e., symptom-directed) physical examinations, including assessment of focused liver signs (presence or absence of edema, ascites, hepatomegaly, splenomegaly, asterixis), skin, and extremities, will be conducted at the time points designated in [Table 2](#) to address any complaints or concerns verbalized by the subject at all other study visits.

Any abnormal findings are to be documented as AEs.

12.1.3. Electrocardiogram (ECG)

Single 12-lead ECGs are to be performed for all subjects at the time points designated in [Table 2](#).

On Day 1, ECGs are to be performed before and 4 hours after the first study drug dose, with the ECG performed prior to PK blood sample collection.

12.1.4. Ophthalmologic Examinations

Ophthalmologic examinations are to be performed for all subjects at the time points designated in [Table 2](#).

Near and far visual acuity is to be assessed by an ophthalmologist using standard measures (e.g., Early Treatment Diabetic Retinopathy Study or similar) in each eye. If the subject wears corrective lenses (e.g., glasses), then visual acuity is to be checked first with corrective lenses and then without correction. (A best-corrected examination is not required.) Note that contact lens wearers are to abstain from contact lens use during study drug treatment.

A slit lamp examination (biomicroscopy), including examination of the eyelids, conjunctiva, cornea, anterior chamber, iris, and lens, is to be performed after completion of visual acuity testing for the determination of corneal health.

If a subject experiences a treatment-emergent ophthalmologic abnormality, an ophthalmologic examination should be performed within 24 to 48 hours or next business day after symptom onset to evaluate the abnormality.

12.1.5. Safety Laboratory Assessments

Blood and urine samples are to be collected for hematology, clinical chemistry, and urinalysis according to the time points designated in [Table 2](#). The following safety laboratory parameters are to be measured:

Hematology

Hematocrit	Platelet count
Hemoglobin	White blood cell count with differential
Red blood cell count	Absolute neutrophil count

Coagulation Studies

Prothrombin time	Activated partial thromboplastin time
INR	

Chemistry (Fasting)

Chloride	Carbon dioxide
Sodium	Potassium
Blood urea nitrogen	Calcium
Creatinine	Magnesium
Albumin	Glucose
Total protein	Alkaline phosphatase
AST*	ALT*
Indirect and direct bilirubin	

Creatine phosphokinase (total and fractionated)
(screening and baseline only)

*AST and ALT collected as part of the clinical chemistry panel are also applicable for efficacy assessments.

Urinalysis

Specific gravity	Protein
pH	Ketones
Blood	Microscopic examination of sediment
Glucose	

LFTs determined as part of the clinical chemistry panel will be used for the assessment of the secondary efficacy endpoint.

Clinical laboratory evaluations are to be repeated as necessary during treatment at a schedule determined by the Investigator, based on the subject's clinical status.

Laboratory abnormalities that are considered by the Investigator to be clinically significant for a particular subject are to be reported as an AE.

12.2. Adverse and Serious Adverse Events

12.2.1. Definition of Adverse Events

12.2.1.1. Adverse Events (AE)

An AE is any untoward medical occurrence in a patient or clinical investigation subject administered a pharmaceutical product, and which does not necessarily have to have a causal relationship with this treatment. An AE can therefore be any unfavorable and unintended sign (including abnormal laboratory findings), symptom, or disease temporally associated with the use of an investigational product, whether or not related to the investigational product.

An unexpected AE is any event for which the nature or severity is not consistent with the information in the current Investigator's Brochure.

All AEs that occur from screening (i.e., after the ICF is signed) through 28 days after the last dose of study drug, whether or not they are related to the study drug, are to be reported in the eCRF.

12.2.1.2. Serious Adverse Event (SAE)

An AE or suspected adverse reaction is considered serious if, in the view of either the Investigator or Sponsor, it:

- Results in death.
- Is life-threatening. Life-threatening means that the subject was at immediate risk of death from the reaction as it occurred, i.e., it does not include a reaction which hypothetically might have caused death had it occurred in a more severe form.
- Requires in-patient hospitalization or prolongation of existing hospitalization. Hospitalization admissions and/or surgical operations scheduled to occur during the study period, but planned prior to study entry are not considered AEs if the illness or disease existed before the subject was enrolled in the study, provided that it did not deteriorate in an unexpected manner during the study (e.g., surgery performed earlier than planned). Additional exclusions to SAE reporting include hospitalizations for:
 - Elective procedures.
 - Social/administrative reasons in the absence of an AE.
 - Expected deterioration caused by progression of the underlying disease.
- Results in persistent or significant disability/incapacity. Disability is defined as a substantial disruption of a person's ability to conduct normal life functions.
- Is a congenital anomaly/birth defect.

- Is an important medical event. An important medical event is an event that may not result in death, be life-threatening, or require hospitalization but may be considered an SAE when, based upon appropriate medical judgment, it may jeopardize the subject and may require medical or surgical intervention to prevent one of the outcomes listed in the definitions for SAEs. Examples of such medical events include allergic bronchospasm requiring intensive treatment in an emergency room or at home, blood dyscrasias or convulsions that do not result in in-patient hospitalization, or the development of drug dependency or drug abuse.

All SAEs that occur after any subject has been enrolled, before treatment, during treatment, or within 28 days following the cessation of treatment, whether or not they are related to the study drug, must be recorded on forms provided by Sagimet Biosciences, or designee.

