12.2.2.2. Relationship to Study Drug

The causal relationship of each AE to study drug will be determined by the Investigator according to best medical judgment, as follows:

- Definitely related:** This category applies when, after careful medical consideration, there is almost no consideration of other causation.
- Probably related:** There is a clinically plausible time sequence between onset of the AE and study drug administration. The AE is unlikely to be caused by a concurrent and/or underlying illness, other drugs, or

¹. If a life-threatening (Grade 4) adverse event is *immediately* life-threatening, the event is, by definition, serious and is to be reported as described in [Section 12.2.4](#).

procedures. If applicable, the AE follows a clinically consistent resolution pattern upon withdrawal of study drug.

Possibly related:

There is a clinically plausible time sequence between onset of the AE and study drug administration, but the AE could also have been caused by the concurrent/underlying illness, other drugs, or procedures. Information regarding study drug withdrawal may be lacking or unclear. “Possible” should be used when study drug administration is one of several biologically plausible causes of the AE.

Unlikely related:

The AE is most likely due to a non-study drug-related cause. However, association with the study drug cannot be completely ruled out.

Unrelated:

Another cause of the AE is most plausible and a clinically plausible temporal sequence is inconsistent with the onset of the AE and study drug administration and/or a causal relationship is considered biologically implausible.

If the relationship between the AE/SAE and study drug is determined to be “possible”, “probable”, or “definite”, the event will be considered to be treatment-related for the purposes of expedited regulatory reporting and safety analyses.

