12.2.4. Reporting Serious Adverse Events

All SAEs (related and unrelated) occurring from screening through 28 days after the last study drug dose are to be reported. Any suspected case of pneumonitis, considered an adverse events of special interest, should be reported in the same manner as an SAE.

The Investigator must report all SAEs within 24 hours of discovery via the EDC system, which will trigger email notifications to the ProSciento, Inc., Medical Monitor/Safety team. (In the event the EDC system is not available, then SAE reports must be emailed to [contact].)

The Investigator must complete and electronically sign and date the SAE pages of the eCRF and verify the accuracy of the information recorded on the SAE pages with the corresponding source documents.

Additional follow-up information, if required or available, should be submitted within the EDC system within one business day of receipt and this should be completed on a follow-up SAE form and placed with the original SAE information and kept with the appropriate section of the eCRF and/or study file.

Sagimet Biosciences is responsible for notifying the relevant regulatory authorities of certain events. It is the Investigator's responsibility to notify the IRB of all SAEs that occur at his or her study center. Investigators will also be notified of all unexpected, serious, drug-related events (7/15 Day Safety Reports) that occur during the clinical study. Each study center is responsible for notifying its IRB of these additional SAEs.

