15.2. Case Report Form Completion

The Sponsor or designee will provide the study centers with eCRFs for each subject.

eCRFs will be completed for each study subject. It is the Investigator's responsibility to ensure the accuracy, completeness, and timeliness of the data reported in the subject's eCRF. Source documentation supporting the eCRF data should indicate the subject's participation in the study and should document the dates and details of study procedures, AEs, and subject status.

The Investigator, or designated representative, should complete the eCRF as soon as possible after information is collected, preferably on the same day that a subject is seen for an

examination, treatment, or any other study procedure. Any outstanding entries must be completed immediately after the final examination. An explanation should be given for all missing data.

The Investigator must electronically sign and date the Investigator's Statement at the end of the eCRF to endorse the recorded data.

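### The SAE definition exempts hospitalisation for expected progression of the underlying disease, with no exception for hepatic events or suspected drug-induced liver injury, in a trial where the underlying disease is a liver disease

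*Protocol*

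**What the plan says.** Protocol section 12.2.1.2 defines an SAE as an event meeting one of the usual seriousness criteria "in the view of either the Investigator or Sponsor". Under the hospitalisation criterion it adds a list opening "Additional exclusions to SAE reporting include hospitalizations for". The list has three entries: elective procedures, social or administrative admissions without an AE, and "Expected deterioration caused by progression of the underlying disease". The third entry carries no further qualification.

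The surrounding rules are these:

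- **Reporting (section 12.2.4).** "All SAEs (related and unrelated) occurring from screening through 28 days after the last study drug dose are to be reported", and "The Investigator must report all SAEs within 24 hours of discovery via the EDC system". One harm has its own route whether or not it is serious: "Any suspected case of pneumonitis, considered an adverse events of special interest, should be reported in the same manner as an SAE".
- **Causality (section 12.2.2.2).** The category of possible relationship "should be used when study drug administration is one of several biologically plausible causes of the AE". An event in that category counts as treatment-related for expedited reporting and for the safety analyses.
- **DILI (section 8.6 and Appendix A).** Drug is interrupted or stopped, other causes are investigated, liver tests are repeated and the subject is closely observed. Neither place calls for an SAE report or a 24-hour notice.
- **Endpoint (Protocol section 6.4.2, SAP section 4.2).** The proportion of subjects with SAEs is a stated safety endpoint. SAP section 8.5.1 adds an SAE listing.
- **Blinding (section 9.9).** Site personnel other than those conducting or interpreting imaging know the treatment assignment.

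**The concern.** The exclusion places a judgement about cause inside the test for seriousness. Elsewhere the protocol keeps the two apart: seriousness decides whether an event is reported within 24 hours, and relationship to drug is graded separately. Here, a site that regards a liver admission as NASH progression can conclude that it is not an SAE at all. The causality scale, which would call the event possibly related if drug were one plausible cause, then has no effect on expedited reporting.

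The liver is where this matters most. Effects on ALT and AST are named in the primary safety objective (section 6.1). A hepatic drug reaction and a worsening of NASH may also look alike at presentation, so the ambiguity falls on a harm the trial sets out to detect. At stake are prompt sponsor awareness of a possible DILI case and a complete SAE count in a small trial.

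**Working it through.** The point is one of wording, so the check sets the relevant sections side by side. The plan gives no figure to reproduce.

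**1. Is there an exception anywhere?** These places were read for a hepatic or DILI carve-out: Protocol sections 6.4.2, 7.1, 7.2, 8.6, 8.7, 12.2.1.2, 12.2.3, 12.2.4 and Appendix A; SAP sections 4.2, 8.5 and 8.5.1; and SAP Addendum 1. None contains one.

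**2. Path of a liver admission the site attributes to NASH**

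| Step | Rule | Result |
|---|---|---|
| Serious? | 12.2.1.2, third exclusion | May be judged not serious on the hospitalisation criterion |
| 24-hour report? | 12.2.4, SAEs plus suspected pneumonitis | Not required |
| 7/15-day safety reports? | 12.2.4, serious events only | Not triggered |
| Recorded as an AE? | 12.2.3 | Yes, with a grade |
| In the SAE proportion and listing? | 6.4.2; SAP 4.2 and 8.5.1 | No |
| In the TEAE tables, and Grade 3/4 if so graded? | 6.4.2; SAP 8.5.1 | Yes |

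**3. Which safeguards could bring it back, and how fast?**

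- *Sponsor judgement.* The Sponsor may deem the event serious but must first know of it. For an event not flagged as serious, that starts from the eCRF, where site staff "should complete the eCRF as soon as possible after information is collected, preferably on the same day" (section 15.2). This sets no fixed limit.
- *Other seriousness criteria.* Death, life-threatening events and disability still qualify. The important-medical-event criterion is discretionary, and its examples include no liver injury.
- *Suspension rules (section 7.2).* These run on grade and need one Grade 5 event, two subjects with the same Grade 4 event or three with the same Grade 3 event. A single non-fatal hepatic case triggers nothing.
- *SRC liver review (section 8.7).* This continues, but with no stated clock for an individual case.

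The safeguards keep the event visible. None restores the 24-hour report as a matter of rule.

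**4. Scale per event.** The effect of one missed event on an arm's SAE proportion is 1/n, using planned arm sizes (section 7.1) and the actual Cohort 3 count (SAP Addendum 1, section 2):

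- 50 mg, US and China: n = 30 + 18 = 48; 1/48 = 2.1 points
- 25 mg: n = 30; 1/30 = 3.3 points. In the US-only analysis the same holds for 50 mg (n = 30) and pooled placebo (15 + 15 = 30)
- Pooled placebo, US and China: n = 15 + 24 = 39; 1/39 = 2.6 points
- 75 mg: n = 13; 1/13 = 7.7 points

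These are the arithmetic of a single event and not expected effects.

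**The case against.** The strongest reply is that the bullet does not reach the event in question. It requires deterioration that is both expected and caused by the disease, and a drug-related admission is neither, so the gap needs a misjudgement at the site. Sections 8.2 and 8.3 leave little room for one: cirrhosis, decompensation, low platelets and ALT or AST above five times ULN are all excluded at entry, and dosing lasts 12 to 16 weeks. This stands as a limit on frequency. It also means the bullet has almost no legitimate hepatic use here, so narrowing it loses nearly nothing.

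Appendix A treats the drug as suspect. Where drug is interrupted, restart needs a firm alternative cause and liver tests back at baseline. A DILI case also leads to withdrawal and an Early Termination visit, and would appear among TEAEs leading to discontinuation and in the laboratory shift tables (SAP sections 8.5.1 and 8.5.2). This is correct for subject management and for visibility in the final report. It supplies neither an expedited report nor an entry in the SAE count.

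The pneumonitis route follows an observed signal: six serious episodes in five patients given the drug with paclitaxel (section 5.1). Its absence for DILI is therefore not an inconsistency in itself. That is fair, although section 5.1 reports no pneumonitis with monotherapy, which is how the drug is given here.

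Safety is descriptive, so no formal inference is affected, which is agreed. Finally, section 8.6 refers to a Study Manual that is not among the documents. It may contain a DILI reporting instruction, and this could not be checked.

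**Conclusion.** The concern holds. As written, the protocol allows a liver hospitalisation attributed to NASH to fall outside SAE reporting, and nothing in the available documents overrides that for hepatic events or suspected DILI. The loss is confined to the 24-hour report, any expedited reporting that follows from it, the SAE proportion and the SAE listing. AE recording, grading, Appendix A work-up and SRC liver review continue.

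The conclusion rests on two assumptions: that a site may read *expected* loosely, and that the Study Manual does not close the gap. Frequency cannot be estimated, because the documents give no rate of hepatic admission or of misattribution. Nor can the direction between arms be fixed: staff who know the assignment may blame NASH more readily in placebo subjects. No power or type I error figure changes. This is a worthwhile low-cost correction to safety ascertainment and does not threaten the efficacy conclusions.

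**What to change.** Add to the third exclusion in Protocol section 12.2.1.2:

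> *This exclusion does not apply to hepatic events or suspected DILI; any unplanned hospitalisation for a hepatic event is reported as an SAE.*

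Deleting the bullet would also serve. Either way, attribution is left to the causality scale in section 12.2.2.2 and to the SRC. The cost is one protocol line and at most a few additional SAE reports.
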